#### **6.7.1.2 Absolute change from Baseline in NILC at Week 12 - ITT**

An analysis of covariance (ANCOVA) will be used to compare the absolute change from Baseline in NILC in each treatment group at Week 12, with treatment and analysis center as fixed effects and the Baseline NILC as covariate. Subjects will be analysed according to the treatment they were assigned to (ITT) and missing data will be replaced using a multiple imputation (MI) under missing at random (MAR) assumption.

The adjusted means difference of the comparison of NILC between CB-03-01 and Vehicle and its 95% confidence interval will be derived from the regression model (Table 14.2.2.2).

#### **6.7.1.3 Absolute change from Baseline in ILC at Week 12 - ITT**

An ANCOVA will be used to compare the absolute change from Baseline in ILC in each treatment group at Week 12, with treatment and analysis center as fixed effects and the Baseline ILC as covariate. Subjects will be analysed according to the treatment they were assigned to (ITT) and missing data will be replaced using a multiple imputation (MI) under missing at random (MAR) assumption.

The adjusted means difference of the comparison of ILC between CB-03-01 and Vehicle and its 95% confidence interval will be derived from the regression model (Table 14.2.2.3).

### **6.7.2 Secondary efficacy analysis**

#### **6.7.2.1 Absolute change from Baseline in TLC at Week 12 - ITT**

An analysis of covariance (ANCOVA) will be used to compare the absolute change from Baseline in TLC in each treatment group at Week 12, with treatment and analysis center as fixed effects and the Baseline TLC as covariate. Subjects will be analysed according to the treatment they were assigned to (ITT) and missing data will be replaced using a multiple imputation (MI) under missing at random (MAR) assumption.

The adjusted means difference of the comparison of TLC between CB-03-01 and Vehicle and its 95% confidence interval will be derived from the regression model (Table 14.2.2.4).

#### **6.7.2.2 Percent change from Baseline in NILC at Week 12 - ITT**

An analysis of covariance (ANCOVA) will be used to compare the percent change from Baseline in NILC in each treatment group at Week 12, with treatment and analysis center as fixed effects and the Baseline NILC as covariate. Subjects will be analysed according to the treatment they were assigned to (ITT) and missing percent changes will be calculated using the values obtained from the multiple imputation (MI) under missing at random (MAR) assumption performed for the NILC (see paragraph 6.7.1.2).

The adjusted percent means difference of the comparison of NILC between CB-03-01 and Vehicle and its 95% confidence interval will be derived from the regression model (Table 14.2.2.5).

#### **6.7.2.3 Percent change from Baseline in ILC at Week 12 - ITT**

An analysis of covariance (ANCOVA) will be used to compare the percent change from Baseline in ILC in each treatment group at Week 12, with treatment and analysis center as fixed effects and the Baseline ILC as covariate. Subjects will be analysed according to the treatment they were assigned to (ITT) and missing percent changes will be calculated using the values obtained from the multiple imputation (MI) under missing at random (MAR) assumption performed for the ILC (see paragraph 6.7.1.3).

The adjusted percent means difference of the comparison of ILC between CB-03-01 and Vehicle and its 95% confidence interval will be derived from the regression model (Table 14.2.2.6).

#### **6.7.2.4 Percent change from Baseline in TLC at Week 12 - ITT**

An analysis of covariance (ANCOVA) will be used to compare the percent change from Baseline in TLC in each treatment group at Week 12, with treatment and analysis center as fixed effects and the Baseline TLC as covariate. Subjects will be analysed according to the treatment they were assigned to (ITT) and missing percent changes will be calculated using the values obtained from the multiple imputation (MI) under missing at random (MAR) assumption performed for the TLC (see paragraph 6.7.2.1).

The adjusted percent means difference of the comparison of TLC between CB-03-01 and Vehicle and its 95% confidence interval will be derived from the regression model (Table 14.2.2.7).

### **6.7.3 Sensitivity analyses**

The robustness of the result obtained on the ITT set for the primary endpoints will be tested by performing the following sensitivity analyses.

#### **6.7.3.1 Per Protocol analysis**

##### **6.7.3.1.1 Proportion of subjects in each treatment group with at least a two-point reduction in IGA compared to Baseline AND an IGA score of 0 (clear) or 1 (almost clear) at Week 12 - PP**

A logistic regression model with treatment and analysis center as fixed effects will be used to compare the proportion of subjects in each treatment group with at least a two-point reduction in IGA AND an IGA score of 0 (clear) or 1 (almost clear) at Week 12 ( $\pi_{2p(0,1)}$ ). Subjects will be analysed according to the treatment they were assigned to (PP).

The adjusted odds ratio of the comparison of  $\pi_{2p(0,1)}$  between CB-03-01 and Vehicle and its 95% confidence interval will be derived from the regression model (Table 14.2.3.1).

#### **6.7.3.1.2 Absolute change from Baseline in NILC at Week 12 - PP**

An analysis of covariance (ANCOVA) will be used to compare the absolute change from Baseline in NILC in each treatment group at Week 12, with treatment and analysis center as fixed effects and the Baseline NILC as covariate. Subjects will be analysed according to the treatment they were assigned to (PP).

The adjusted means difference of the comparison of NILC between CB-03-01 and Vehicle and its 95% confidence interval will be derived from the regression model (Table 14.2.3.2).

#### **6.7.3.1.3 Absolute change from Baseline in ILC at Week 12 - PP**

An ANCOVA will be used to compare the absolute change from Baseline in ILC in each treatment group at Week 12, with treatment and analysis center as fixed effects and the Baseline ILC as covariate. Subjects will be analysed according to the treatment they were assigned to (PP).

The adjusted means difference of the comparison of ILC between CB-03-01 and Vehicle and its 95% confidence interval will be derived from the regression model (Table 14.2.3.3).

#### **6.7.3.2 Missing as worst value analysis**

The analyses of sections 6.7.1.1, 6.7.1.2 and 6.7.1.3 will be repeated by replacing missing data according to the Missing as Worst Value (MwV) approach. Subjects will be analysed according to the treatment they were assigned to (ITT) (Table 14.2.3.4, Table 14.2.3.5, Table 14.2.3.6).

#### **6.7.3.3 Worst case analysis**

The analyses of sections 6.7.1.1, 6.7.1.2 and 6.7.1.3 will be repeated by replacing missing data according to the Worst Case (WC) approach. Subjects will be analysed according to the treatment they were assigned to (ITT) (Table 14.2.3.7, Table 14.2.3.8, Table 14.2.3.9).

#### **6.7.3.4 LOCF analysis**

The analyses of sections 6.7.1.1, 6.7.1.2 and 6.7.1.3 will be repeated by replacing missing data according to the Last Observation Carried Forward (LOCF) approach. Subjects will be analysed according to the treatment they were assigned to (ITT) (Table 14.2.3.10, Table 14.2.3.11, Table 14.2.3.12).

#### **6.7.3.5 BOCF analysis**

The analyses of sections 6.7.1.1, 6.7.1.2 and 6.7.1.3 will be repeated by replacing missing data according to the Baseline Observation Carried Forward (BOCF) approach. Subjects will be analysed according to the treatment they were assigned to (ITT) (Table 14.2.3.13, Table 14.2.3.14, Table 14.2.3.15).

#### **6.7.4 Center by treatment interaction**

An analysis of the center by treatment interaction will be performed in order to evaluate the presence of a significant interaction and, in case of a significant interaction is observed, in order to ensure that the primary efficacy results are not driven by extreme centers. Two different analysis of the center by treatment interaction for the primary efficacy results will be performed, one for the analysis centers and one for the original centers.

#### **6.7.4.1 Analysis center by treatment interaction**

The analyses of sections 6.7.1.1, 6.7.1.2 and 6.7.1.3 will be repeated by adding the analysis center by treatment interaction as fixed effect. The reference levels for the effects of the analysis model will be the analysis center with the highest number of subjects and the vehicle treatment, respectively (Table 14.2.3.16, Table 14.2.3.17, Table 14.2.3.18).

If the analysis center by treatment interaction factor is significant (Wald p-value < 0.10) a sensitivity analysis that excludes analysis centers with the extreme efficacy results will be performed to determine the robustness of the treatment effect. Otherwise, the data will be considered to be free of the impact of extreme analysis centers.

The identification of the extreme analysis centers will be based on the Wald p-values of the analysis center by treatment interaction terms.

Analysis centers will be excluded one by one according to the significance of the interaction term (starting from the one with the most significant interaction term). After each exclusion, the analysis will be repeated on the remaining centers until the analysis center by treatment interaction factor is not significant (Wald p-value  $\geq$  0.10).

Upon identification of the extreme analysis center(s), the analyses of sections 6.7.1.1, 6.7.1.2 and 6.7.1.3 will be repeated considering only the remaining analysis centers. Inferences will be based on this analyses in addition to observations regarding the extreme analysis center(s). Conclusions will be presented as appropriate to the findings of the sensitivity analysis.

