## 6.5 Analysis centers

Each center conducted the clinical study under a common protocol. Consistency in study execution at each center was emphasized. The study had to be conducted in such a manner as to have a minimum of 8 ITT subjects enrolled in each of the treatment groups at each center (i.e. 16 ITT subjects enrolled overall). In the event that there are too few subjects in a treatment arm for a center, then this center's data will be combined with another center's data in order to achieve the desired minimum number of subjects per treatment arm. The combining of data across centers will be accomplished by combining data from two or more centers based on geographic and climatic similarities until the minimum number of subjects per treatment arm is achieved. The sequence of combination will be based on the total number of subjects enrolled in each center (combining lowest to 2nd lowest and so on). Combining center data to achieve sufficient subjects per treatment arm will result in the combined centers. These combined centers, as well as individual centers with sufficient subjects per treatment arm, will be referred to as "analysis centers" in the statistical analyses.

Supposing to have  $N$  geographic and climatic areas with  $M_i$  ( $i=1..N$ ) centers for each area, we can write the set of all centers as

$$\{C_{ij}\}_{i=1..N, j=1..M_i}$$

and the set of ordered centers according to the ascending number of enrolled subjects within each geographic and climatic area as

$$\{C_{ij(k)}\}_{i=1..N, k=1..M_i} \mid \forall i, m < n \Rightarrow \#(C_{ij(m)}) \leq \#(C_{ij(n)})$$

Using this notation, each geographic and climatic area  $i$  can have up to  $A_i$  ( $\forall i=1..N, A_i \leq M_i$ ) analysis centers

$$\{AC_{ij}\}_{i=1..N, j=1..A_i}$$

For example

$$\begin{aligned} AC_{i1} &= C_{ij(1)} \cup C_{ij(2)} \cup C_{ij(3)} \\ AC_{i2} &= C_{ij(4)} \cup C_{ij(5)} \\ AC_{i3} &= C_{ij(6)} \\ &\dots \\ AC_{iA_i} &= C_{ij(M_i)} \end{aligned}$$

The definition of the analysis centers will be performed before the database lock during the blind review meeting/conference.

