### **6.7 Efficacy analysis**

Subjects will be analysed according to the analysis center they will be assigned to and to the treatment they were assigned to (ITT, PP).

The original clinical center of the subjects will be used only for the the investigation of center-to-center variability.

The investigator's global assessment scores will be listed ([Listing 16.2.6.1](#)) and summarised by treatment group (CB-03-01 and Vehicle) using contingency tables ([Table 14.2.1.1](#), [Table 14.2.1.2](#)).

The proportion of subjects with at least a two-point reduction in IGA AND an IGA score of 0 (clear) or 1 (almost clear) will be summarised by treatment group (CB-03-01 and Vehicle) using contingency tables ([Table 14.2.1.3](#), [Table 14.2.1.4](#)).

The acne lesion counts will be listed by treatment group ([Listing 16.2.6.2](#)); the values of NILC and ILC and their changes from baseline will be summarised by treatment group (CB-03-01 and Vehicle) using descriptive statistics ([Table 14.2.1.5](#), [Table 14.2.1.6](#)).

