#### **6.7.4.2 Original center by treatment interaction**

The analyses of sections 6.7.1.1, 6.7.1.2 and 6.7.1.3 will be repeated considering the original center as fixed effect and by adding the original center by treatment interaction as fixed effect. The reference levels for the effects of the analysis model will be the center with the highest number of subjects and the vehicle treatment, respectively (Table 14.2.3.19, Table 14.2.3.20, Table 14.2.3.21).

If the original center by treatment interaction factor is significant (Wald p-value < 0.10) a sensitivity analysis that excludes original centers with the extreme efficacy results will be performed to determine the robustness of the treatment effect. Otherwise, the data will be considered to be free of the impact of extreme centers.

The identification of the extreme centers will be based on the Wald p-values of the center by treatment interaction terms.

Centers will be excluded one by one according to the significance of the interaction term (starting from the one with the most significant interaction term). After each exclusion, the

analysis will be repeated on the remaining original centers until the original center by treatment interaction factor is not significant (Wald p-value  $\geq 0.10$ ).

Upon identification of the extreme original center(s), the analyses of sections 6.7.1.1, 6.7.1.2 and 6.7.1.3 will be repeated considering only the remaining original centers. Inferences will be based on this analyses in addition to observations regarding the extreme original center(s). Conclusions will be presented as appropriate to the findings of the sensitivity analysis.

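### SAP 6.7.4 can never name the largest centre as extreme, and for P1 at the planning rates with many centres its non-significant Wald test cannot support an all-clear

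*SAP*

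**What the plan says.** SAP 6.7.4 repeats the three primary analyses with a centre-by-treatment interaction, first for the pooled analysis centres (6.7.4.1) and then for the original centres (6.7.4.2). One aim is to see whether an interaction is present. The other applies if it is significant: "in order to ensure that the primary efficacy results are not driven by extreme centers". The rule has four parts.

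- **Reference level:** "The reference levels for the effects of the analysis model will be the analysis center with the highest number of subjects" in 6.7.4.1 and "The reference levels for the effects of the analysis model will be the center with the highest number of subjects" in 6.7.4.2. Vehicle is the treatment reference.
- **Trigger:** a joint Wald p-value below 0.10 for the interaction factor.
- **Identification:** "The identification of the extreme analysis centers will be based on the Wald p-values of the analysis center by treatment interaction terms", with a parallel sentence in 6.7.4.2. Centres are dropped one at a time, smallest p-value first, until the joint p-value is at least 0.10. The primary analyses are then rerun without them, and inferences draw on the rerun together with comments on the dropped centres.
- **No trigger:** "Otherwise, the data will be considered to be free of the impact of extreme analysis centers" in 6.7.4.1 and "Otherwise, the data will be considered to be free of the impact of extreme centers" in 6.7.4.2.

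On the number of centres, SAP 6.5 sets a minimum of 8 subjects per arm and adds: "The definition of the analysis centers will be performed before the database lock during the blind review meeting/conference". SAP 6.7 says of the unpooled sites: "The original clinical center of the subjects will be used only for the the investigation of center-to-center variability". SAP 2.4 reports 732 subjects at 48 enrolling sites. SAP 6.7.4 gives no rule for zero cells in the logistic model and no power for the interaction test.

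**The concern.** There are two separate faults.

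First, the check is blind to one centre, and that centre carries the most weight in the pooled result. If the largest centre is the outlier, it helps to trigger the procedure, but the procedure can only remove the centres that disagree with it. The rerun estimate then moves towards the outlier.

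Second, for P1 the plan turns a non-significant test into a positive statement about the data. That is reasonable only if the test could have been significant. About 0.0217 x 366 = 7.9 vehicle successes are expected in the whole trial. Spread over 24 or more centres, they leave most centres with an empty cell, and there a Wald statistic carries almost no information.

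At stake is the credibility of a stated robustness check, not the primary conclusion.

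**Working it through.** **Inputs from the documents.** P1 rates 14.00% and 2.17%, from 3/24 and 0/22 with 0.5 added to each cell (SAP 4.3.1). P3 difference -15 - (-10) = -5, SD 17 (SAP 4.3.3). 732 subjects at 48 sites, 1:1 (SAP 2.4), so 366 per arm and 15.25 per site. Joint test at 0.10 (SAP 6.7.4). The minimum of 16 per analysis centre allows at most 45 (732/16 = 45.75). Centre sizes and outlying effects are not in the documents; those below are assumptions.

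**The plan's own figure.** The SAP 4.3.1 formula gives N = (1.960 + 1.838)² / (ln 7.3256)² x [1/(0.14 x 0.86) + 1/(0.02174 x 0.97826)] = 14.43/3.966 x (8.31 + 47.02) = 201.3, rounded up to 202 as stated. There is no stated figure for the interaction test to reproduce.

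**Step 1: coding.** With K centres the model has K-1 interaction terms. Under reference coding each is a centre's effect minus the largest centre's effect. Under effect coding each is a centre's effect minus the unweighted mean. The largest has no term under either. It stays the largest after every exclusion, so it is the reference at each pass. The joint test does not depend on the choice of reference.

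**Step 2: P3 consequence.** Layouts per arm: 23x15+21, 34x10+26 and 47x7+37 (24, 35 and 48 centres; largest 5.7%, 7.1% and 10.1% of subjects). 4,000 trials per scenario, effect -5 elsewhere. The expected full estimate is -5 + share x (outlier effect + 5). At -25 this runs from -5 - 0.057 x 20 = -6.1 to -5 - 0.101 x 20 = -7.0. Estimates in the table are for triggered trials.

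| Largest centre | Trigger | Full estimate | After exclusions, reference coding | After exclusions, effect coding |
|---|---|---|---|---|
| -5 (no outlier) | 10-11% | | | |
| -10 | 12-13% | | | |
| -15 | 22-24% | -5.7 to -6.0 | -6.6 to -7.0 (shift 0.9-1.4; over all trials 0.2-0.3) | shift 0.1-0.5 (over all trials 0.03-0.10) |
| -25 | 64-74% | -6.2 to -7.0 | -9.4 to -11.6 | -9.1 to -10.8 |

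The largest centre was removed in 0 of 876, 861 and 952 triggered trials at -15, and in 0 of 2,545, 2,615 and 2,950 at -25. At -25, 6-8 ordinary centres were removed. A separate simulation shows that the blind spot is specific to the reference (24 centres, largest with 60 subjects, outlier at -30). With the largest as outlier, the test triggered in 95.5% of runs and on average 16.2 ordinary centres were removed. With another centre as outlier and the rule triggered, that centre went first in 89%, with 1.3 centres removed on average.

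**Step 3: P1 sparseness.** The probability that a centre with n per arm has no success in at least one arm is 1 - (1 - 0.86^n)(1 - 0.9783^n): 0.89, 0.75 and 0.52 at n = 8, 15 and 30. With equal sizes, about 6.1 of 24 centres, or 5.1 of 48, have four non-empty cells. The joint statistic must exceed 32.0 on 23 df, or 59.8 on 47 df. In direct maximum-likelihood fits, a centre with 100% success on active and 0% on vehicle had a median term p-value of 0.997 (24 centres) and 0.998 (48).

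The joint test fired in 0 of 20,000 runs per setting at 24, 30, 35 and 48 centres (layouts of Step 2, plus 29x12+18), with the largest centre at 80% or 90% active success, or at 40%, 60% or 80% vehicle success. With equal-sized centres it also fired in 0 of 20,000 at 24, 30, 36, 45 and 48 centres, under homogeneity and five heterogeneous patterns.

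**Step 4: what goes unseen.** Median Mantel-Haenszel odds ratio, without and with the largest centre:

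- Largest at 80% active: 7.5 becomes 10.0 (24 centres) or 12.0 (48), a factor of 10.0/7.5 = 1.3 or 12.0/7.5 = 1.6.
- Largest at 60% vehicle: 7.5 becomes 2.8 (24) or 1.9 (48), a factor of 7.5/2.8 = 2.7 or 7.5/1.9 = 3.9, towards the null.

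**Step 5: where the P1 test can fire.**

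- 12 centres: 3-13% (active 80-90%), 76% (vehicle 60%).
- 18 centres: 2.6% (vehicle 60%).
- 24 centres with a largest of 44 per arm: 0.7% (vehicle 60%), 18% (vehicle 80%).
- Higher assumed rates, best of the five patterns at 24 equal centres: 19% at 20%/10% and 92% at 30%/15%. At 48 centres, at most 0.01% for either.

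**The case against.** The strongest reply is that little depends on this. SAP 6.7.4 is a sensitivity analysis. Its search for extreme centres is conditional on a significant interaction, and it leaves conclusions to judgement. Nothing in the documents points to an outlying centre. For P3 the drift is material only for an implausible outlier. With vehicle at -10, an effect of -25 means a mean active change of -35, when subjects may enter with as few as 30 inflammatory lesions. All of this stands and limits the weight of the point. It does not rescue an identification rule that excludes one centre by construction, or an all-clear from a test that cannot fail.

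The P1 planning rates are also soft, since 0/22 is compatible with a much higher vehicle rate, and higher rates restore power at 24 centres. That stands for the analysis centres. At 48 sites the power stayed negligible at every rate tried.

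A reader might infer more than the documents support:

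- **That the primary result is unsafe.** It is not affected: SAP 6.7.1 and the hierarchy in 4.2 do not use this procedure.
- **That the P1 test can never fire.** It can, with fewer centres, a dominant centre or much higher success rates.
- **That the P1 rule could hide a several-fold exaggeration of efficacy.** The threefold to fourfold shift arises only from a vehicle-side outlier and runs towards the null. In the favourable direction the factor is 1.3-1.6.
- **That the largest centre escapes the test altogether.** It contributes to the joint trigger; only identification and exclusion miss it.

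**Conclusion.** Both faults hold. The first is exact: barring a tie, the largest centre cannot be identified or excluded in 6.7.4.1 or 6.7.4.2, under reference or effect coding. The SAP does not fix the coding, and effect coding gives much less drift at -15 but similar drift at -25.

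The second is conditional. It needs P1 rates near 14% and 2.17%, and about 24 or more analysis centres with none dominant. The 48-site analysis meets the centre-number condition. Whether the pooled analysis does will be known only after the blind review.

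The sizes are illustrations for assumed layouts with complete data. Multiple imputation and its Type-III pooling were not simulated; the reference has no term in any imputed data set, but imputed successes could fill some empty P1 cells. The odds ratios are Mantel-Haenszel medians, not the SAP's adjusted, imputed estimates. The correction should be made, because the rules as written can mislead and it costs little.

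**What to change.** 1. **P2 and P3, in both 6.7.4.1 and 6.7.4.2:** replace the identification sentence with: *For every center, including the largest, the treatment effect will be contrasted with the subject-weighted average effect in all other centers still in the analysis; centers are excluded starting from the smallest contrast p-value.* In the Step 2 simulations this removed an extreme largest centre in 52-62% of triggered trials at -15 and 96-99% at -25. It dropped 1.2-1.4 centres on average and gave final estimates of -5.1 to -5.2 and -4.9. It still misses 38-48% of triggered trials at -15, so it is an improvement and not a guarantee.
2. **Delete** the sentences "Otherwise, the data will be considered to be free of the impact of extreme analysis centers" and "Otherwise, the data will be considered to be free of the impact of extreme centers".
3. **P1:** drop the Wald trigger and the exclusion loop. Report the odds ratio with each centre left out in turn, from the same imputed data sets as 6.7.1.1. An exact conditional (Zelen) homogeneity test on observed Week 12 data is an optional supportive output, labelled as outside the imputation framework. In simulation at 0.10 with 24, 35 and 48 centres it fired in 8-9% with no outlier, 86-96% with the largest at 80% versus 2.17%, and 96-99% at 14% versus 60%. An inverse-variance risk-difference test is not a substitute. It is undefined where neither arm has a success, which has probability (0.86 x 0.9783)^8 = 0.25 in a centre with 8 per arm.

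The cost is SAP wording and minor programming before database lock, and a less reassuring statement in the report. Data collection, alpha and the primary tests do not change.
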